### **11.6.4 Differences in the medians of PROMs at Weeks 12 and 24 between Arms B and C**

As described in section 11.6.3 descriptive statistics will also be provided for Arms B vs C.

### **11.6.5 Differences in the proportion of participants achieving imaging remission at Week 24 between Arms A and B**

The proportions of patients in imaging remission (PD=0) at Week 24 will be summarised descriptively by arm and overall for Arms A and B.

### **11.6.6 Difference in the proportion of participants achieving imaging remission at Week 24 between Arms B and C**

As described in section 11.6.5, descriptive summaries will also be provided for Arm C.

### **11.6.7 Difference in the proportion of participants achieving normalized T-cell status post-baseline**

The difference in the proportion of patients in Arm B vs. Arm C will be summarised descriptively by arm and overall.

### **11.6.8 Difference in the proportion of participants achieving sustained clinical remission between study arms**

This endpoint will be assessed for Arms A vs B and again for Arms B vs C.

The model detailed in the primary analysis (section 11.5.1) will be utilised where the response variable is replaced with a binary indicator of sustained clinical remission. The proportions achieving sustained clinical remission and unadjusted and adjusted odds ratios with corresponding 2-sided 95% CIs will be reported for Arms A vs B and Arms B vs C. In addition, the p-value will be reported for Arms A vs B and additional CIs (75%, 85% and 90%) will be reported for Arms B vs C.

### **11.6.9 Difference in cumulative corticosteroid use up to and including Week 24 between study arms**

Descriptive summaries of the corticosteroid dose at each visit by arm will be provided. The difference in the unadjusted average (mean and median) cumulative amount of corticosteroid use up to and including at the 24 weeks visit between study arms (Arm A vs. Arm B and Arm B vs. Arm C) will also be included.

## 11.7 Safety analyses

### 11.7.1 Adverse events

Adverse events for this trial will be summarised descriptively using the safety set. The number of serious and non-serious adverse events over the 24-week follow-up period, as well as the number and percentage of participants these events occurred in, and the exposure by 100 patient-years will be reported for each trial group.

The number of serious adverse events in each trial group will be broken down by reason for classification as serious adverse event and relationship of event to treatment and outcome. The number of non-serious adverse events in each trial group will also be broken down by relationship of non-serious adverse event to treatment and outcome.

### 11.7.2 Laboratory measurements

Laboratory parameters from haematology (full blood count) and biochemistry tests (eGFR, LFT, urea and electrolytes) will be summarised descriptively by visit for each trial group and overall.

## 12 Exploratory analyses

### 12.1 Optimal naïve CD4 T-cell frequency cut-off

Previously published research suggested that the optimal naive CD4 T-cell frequency cut-off for prediction of response to MTX monotherapy was equivalent to the expected value for the patient's age. We will verify this by pooling the patients in arms A and B and using non-parametric ROC curve analysis, taking clinical remission at 6 months as the reference variable and age-corrected baseline naive CD4 $\pm$  T-cell frequency as the classification variable. Area under the ROC curve and the 95% confidence interval will be presented. The point at which the Youden Index ( $J = \text{sensitivity} + \text{specificity} - 1$ ) is maximised will be chosen as the optimal cut-off. A plot of the baseline CD4 T-cell against the continuous DAS28ESR index at 6 months will be provided. We may additionally investigate whether there is evidence that baseline DAS28ESR affects the accuracy of classification by including it as a covariate in a secondary ROC analysis.

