12.5.3. Other analyses

Sensitivity analyses of the primary and secondary outcomes will be repeated in the per protocol set.

Previously published research suggested that the optimal naive CD4 T-cell frequency cut-off for prediction of response to MTX monotherapy was equivalent to the expected value for the patient's age. We will verify this by pooling the patients in arms A and B and using non-parametric ROC curve analysis, taking clinical remission at 6 months as the reference variable and age-corrected baseline naive CD4 \pm T-cell frequency as the classification variable. Area under the ROC curve and the 95% confidence interval will be presented. The point at which the Youden Index ($J = \text{sensitivity} + \text{specificity} - 1$) is maximised will be chosen as the optimal cut-off. We will additionally investigate whether there is evidence that baseline DAS28 affects the accuracy of classification by including it as a covariate in a secondary ROC analysis.

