## **9. Sample Size**

We will allocate the patients to arm A if the patient's naive CD4+ T-cell frequency is normal for their age and gender. In our previous pilot study 42% of comparable RA patients had abnormal frequency values, of whom 25% responded to MTX at 6 months compared to 68% of those with normal values.

Those with abnormal values will be (randomly permuted block) randomised 1:1 to arm B or C, therefore this would result in an approximate 2.75:1 ratio of patients in arms A and B. For the primary outcome of clinical remission at 24 weeks, at the 5% level of significance, to achieve 80% power to detect a difference between the target proportions of patients achieving clinical remission in arms A (68%) and B (25%) [3], a total of 53 patients would be required, assuming binary logistic regression with a variance inflation factor of 1.05 estimated from pilot data. We will increase the sample size to n=60 to account for 10% drop-out. The total number needed to be recruited to the study would therefore be 76 (44 in arm A, 16 in arm B and 16 in arm C). To have a more robust estimate of the proportion of clinical remission in arm B and C, recruitment will continue until at least 34 and no more than 60 patients with abnormal T-cell values have been randomised 1:1 to arm B or C, and there are at least 46 patients in arm A. Thus, the total sample size for the study is anticipated to be between 76 (approximately A=44, B=16, C=16) and 106 patients (approximately A=46, B=30, C=30). In the case where recruitment within Arm A is disproportionately recruiting more than Arm B or C, recruitment will stop within Arm A once minimum recruitment number has been reached.

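### The ROC analysis of the T-cell cut-off pools arms A and B without weights, although arm B holds only half of the abnormal patients, so it should be reported with a weighted version beside it

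*SAP*

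**What the plan says.** SAP 12.1, among the exploratory analyses, and Protocol 12.5.3 describe the same check of the arm-defining cut-off: "We will verify this by pooling the patients in arms A and B and using non-parametric ROC curve analysis". Remission at 6 months is the reference, and age-corrected baseline naive CD4+ T-cell frequency is the classifier. The AUC is to be given with a 95% confidence interval, and the point where the Youden index is "maximised will be chosen as the optimal cut-off". Neither section mentions weights or the absence of arm C.

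SAP 9 and Protocol 12.9 describe how patients reach the two arms. A normal result leads to arm A. For the rest, "Those with abnormal values will be (randomly permuted block) randomised 1:1 to arm B or C". The documents state the consequence: "this would result in an approximate 2.75:1 ratio of patients in arms A and B". The same sections give planned sizes from A=44, B=16, C=16 to A=46, B=30, C=30. They also provide that, if arm A fills disproportionately, "recruitment will stop within Arm A once minimum recruitment number has been reached".

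**The concern.** Entry to the pooled A+B sample depends on the marker that the ROC evaluates. While arm A is open, every enrolled normal patient is included but only half of the abnormal ones. Arm C cannot be added back, because those patients receive etanercept and their remission status does not measure response to methotrexate.

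Selection on the marker leaves the remission risk at a given marker value unchanged. It does change the marker distribution among remitters and non-remitters, from which sensitivity, specificity, AUC and the Youden index are built. An unweighted analysis therefore describes an artificial mix and not the clinic population in which the cut-off would be used. The analysis is meant to confirm the line that defines the arms, and readers may compare it with the earlier sensitivity and specificity of 79% and 81% in Protocol 1.1. A low specificity could then be taken as poor replication when part of it comes from the design.

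**Working it through.** **Inputs (SAP 9, Protocol 12.9).** "In our previous pilot study 42% of comparable RA patients had abnormal frequency values", so 58% were normal. Of the abnormal patients, "25% responded to MTX at 6 months compared to 68% of those with normal values". A normal result predicts remission.

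**The plan's own figures reproduce.** The A:B ratio is 0.58/(0.42/2) = 0.58/0.21 = 2.76, against 2.75 stated. The pooled-variance two-proportion formula gives a total of 49.94; × 1.05 = 52.43, rounded up to the stated 53. In the source population the normal:abnormal ratio is 58:42 = 1.38.

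**Formulas at the age-expected line,** with a normal and b abnormal patients:
- Se = 0.68a/(0.68a + 0.25b)
- Sp = 0.75b/(0.75b + 0.32a)
- J = Se + Sp − 1

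| Sample | Se | Sp | J |
|---|---|---|---|
| Source population, 58:42 | 0.3944/0.4994 = 79.0% | 0.315/0.5006 = 62.9% | 0.42 |
| Unweighted, 44:16 | 29.92/33.92 = 88.2% | 12/26.08 = 46.0% | 0.34 |
| 44:16 with B weighted by 2 (44:32) | 29.92/37.92 = 78.9% | 24/38.08 = 63.0% | 0.42 |
| Unweighted, 46:30 | 31.28/38.78 = 80.7% | 22.5/37.22 = 60.5% | 0.41 |
| 46:30 with B weighted by 2 (46:60) | 31.28/46.28 = 67.6% | 45/59.72 = 75.4% | 0.43 |

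At 44:16 the distortion is about +9 points in sensitivity and −17 in specificity, and weighting B by 2 removes it. At 46:30 it is about 2 points. There, 60 abnormal patients would be accompanied by about 60 × 58/42 = 83 normal ones, of whom 46 (about 55%) are in arm A, so early closure nearly offsets the loss to arm C. A fixed weight of 2 would then overcorrect.

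**Direction.** If the true abnormal share were 35% (an assumption), the population values would be Se = 0.442/0.5295 = 83.5% and Sp = 0.2625/0.4705 = 55.8%. The 46:30 sample would still show 80.7% and 60.5%, so the bias would reverse.

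**Cut-off and AUC.** With smoothly rising risk, the Youden optimum lies where the risk at the marker value equals the remission prevalence in the sample. That prevalence is 49.9% in the source population and 56.5% (33.92/60) at 44:16, so the optimum moves up. In an assumed model (normal marker, logistic risk, calibrated to 42%, 25% and 68%):

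| Mix | Youden cut-off above the line | AUC |
|---|---|---|
| Source population | +0.20 SD | 0.790 |
| 44:16 unweighted | +0.40 SD | 0.774 |
| 46:30 unweighted | +0.24 SD | 0.788 |

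**Precision.** Simulating this model at 44:16, the AUC has a standard deviation of about 0.06, against a bias of about 0.02. The Youden cut-off has a standard deviation of about 0.3 SD units unweighted and 0.34 with B weighted by 2. Its root mean squared error is about 0.35 either way.

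**The case against.** The strongest reply is that the large figures are not planned outputs. SAP 12.1 commits to an AUC, a Youden cut-off and a plot, not to sensitivity and specificity at the age-expected line. The committed outputs move less, and by less than their sampling error. For the cut-off, weighting exchanges bias for variance with no gain in mean squared error at this size. The analysis is exploratory, and no hypothesis, allocation or decision rule depends on it. All of this stands, and it limits the weight of the point. It does not justify leaving out a correction for a sampling fraction set by the design, particularly when a ROC curve invites readers to take sensitivity and specificity from it.

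A reader might infer that the unweighted analysis would wrongly show the age-expected line not to be optimal. The documents do not support that. In the smooth-risk model the true optimum is already 0.20 SD above the line, so a finding to that effect would not be wrong. If risk instead steps exactly at the line, the optimum stays there without weights, although sensitivity and specificity are still distorted.

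A reader might also infer that sensitivity is always overstated and specificity always understated. That holds at 44:16 on the pilot rates, but not over the whole planned range and every plausible abnormal share.

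A further limit concerns the remedy. The screening-log items in Protocol 6.5.1 do not include T-cell status, so normal patients seen after arm A closed may not be countable.

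**Conclusion.** The point holds as a moderate one about an exploratory analysis. The pooled sample is selected on the marker, the plan does not correct for this, and with arm A open throughout the effect at the age-expected line is large: 88%/46% in place of 79%/63%. These figures rest only on the plan's 42%, 25% and 68%. The AUC change (about 0.02) and the cut-off shift (about 0.2 SD) rest in addition on the assumed normal/logistic model; the shift requires risk to rise smoothly with the marker and is smaller than the sampling error. The size, and possibly the sign, depend on the realised A:B mix and the true abnormal share. The primary A versus B comparison is not affected, because selection depends only on the marker and leaves the remission risk at each marker value unchanged.

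**What to change.** In SAP 12.1, add a ROC weighted by the inverse of the sampling fraction and report it beside the unweighted one. Give bootstrap confidence intervals for the AUC, the Youden cut-off, and sensitivity and specificity at the age-expected line.

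- **Arm B weight:** abnormal patients randomised divided by patients in B, about 2.
- **Arm A weight:** 1 while arm A was open.
- **If arm A closed early:** either weight A by eligible normal patients divided by those enrolled, if T-cell status was recorded for them, or restrict the weighted analysis to the period when arm A was open. Do not apply a fixed weight of 2 to the whole sample in that case.

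State the realised A:B:C counts and any closure date with the results. The cost is a few lines of code and SAP wording, and slightly wider intervals. Restricting to the open period also discards some data. For the cut-off at about 60 patients, the reduction in bias is offset by variance, so the text should say that its location will be imprecise in either version.

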### **7.2.4 Difference in the proportion of participants achieving normalized T-cell status post-baseline**

The difference in the proportion of patients with normal naïve CD4+ T-cells at 24 weeks for patients with abnormal baseline naïve CD4+ T-cells receiving MTX with T2T care (Arm B) vs. etanercept + MTX (Arm C) will be calculated.

Naïve CD4+ T-cells will be measured via cell surface antigen detection by 8-colour flow cytometry. The CD4+ T-cells will first be identified by staining for the CD and CD4 markers. Naïve cells will be identified based on the high expression of CD45RB and positivity for CD45RA and CD62L. Also included in this panel will be T-regulatory cells (Treg) and inflammation related cells (IRC's).

Patients' naïve T-cell frequency (%) will be compared to the level expected for their age according to the following formula derived from 106 healthy controls [1]:  $(-0.54 * age) + 63.19$ .

A patient whose naïve T-cell level is at or above this value will be considered to have a normal T-cell result; a patient with levels below the age-expected value will be considered to have an abnormal result.

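### The exploratory ROC analysis is said to verify the age-expected cut-off, but its only rule picks the sample Youden maximum, with no interval for that point and no accuracy reported at the pre-set cut-off

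*SAP*

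**What the plan says.** SAP 12.1 recalls earlier work suggesting that the best cut-off equals the value expected for the patient's age, and continues: "We will verify this by pooling the patients in arms A and B and using non-parametric ROC curve analysis". The reference variable is remission at 6 months and the classifier is the age-corrected baseline frequency. The point at which the Youden index J = sensitivity + specificity - 1 "is maximised will be chosen as the optimal cut-off". On uncertainty it says: "Area under the ROC curve and the 95% confidence interval will be presented". The SAP adds a plot of baseline T-cell level against continuous DAS28ESR. Protocol 12.5.3 contains the same cut-off rule.

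The cut-off under test is fixed elsewhere. Protocol 8.2 and SAP 7.2.4 give 63.19 - 0.54 × age, and: "A patient whose naïve T-cell level is at or above this value will be considered to have a normal T-cell result". On the age-corrected scale this is the value 0.

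Neither section gives an interval for the Youden point, an optimism correction, accuracy at 0, or a criterion for when the cut-off counts as verified. The bootstrapping in SAP 11.5.1 and 11.5.1.2 is for differences in proportions, not for this analysis.

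**The concern.** To verify a pre-set threshold, one evaluates that threshold. The plan instead searches for the best threshold in the sample and names the result optimal. A maximum taken over 60 to 76 observed values moves with sampling noise, so it will usually differ from 0 even when 0 is correct. J at the maximum is also too high on average, because the same data chose the point. The AUC does not help here: it summarises all cut-offs and says nothing about any one of them.

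The stake is interpretive. SAP 5 gives confirming and validating T-cell quantification as an aim, and a later trial or clinic would need a threshold. As planned, the report would name an optimal cut-off with no stated uncertainty, and a reader could not tell whether a difference from 0 means anything.

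**Working it through.** **Inputs from the documents (SAP 9).** Arm sizes of A=44, B=16 at the low end and A=46, B=30 at the high end, so pooled A+B is 44 + 16 = 60 to 46 + 30 = 76. The stated recruitment floor (at least 34 abnormal and 46 in arm A) implies about 46 + 17 = 63, which does not change the conclusion. Abnormal share 42%; remission 68% in A and 25% in B.

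**The plan's own figure.** No precision is stated for the cut-off. The primary sample size reproduces: the pooled two-proportion formula at 2.75:1, two-sided 5% and 80% power gives 49.94 in total; × 1.05 = 52.43, rounded up to 53. Then 53/0.9 = 58.9, so 59 against the stated 60.

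**Expected J at 0.**
- 44+16: remitters 44 × 0.68 = 29.92 and 16 × 0.25 = 4. Sensitivity 29.92/33.92 = 0.882; specificity 12/(12 + 14.08) = 0.460; J = 0.342.
- 46+30: remitters 31.28 and 7.5. Sensitivity 31.28/38.78 = 0.807; specificity 22.5/(22.5 + 14.72) = 0.605; J = 0.411.

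**Simulation (assumed model).** The age-corrected marker is normal with 42% below 0. Remission is 0.68 at or above 0 and 0.25 below, a step that makes 0 exactly optimal. There were 5,000 trials per setting, and J was maximised over the sample.

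| A+B | 95% range of chosen point (marker SD) | Mean maximised J | Mean sample J at 0 | Difference |
|---|---|---|---|---|
| 44+16 | -0.30 to +0.77 | 0.394 | 0.347 | 0.047 |
| 46+30 | -0.29 to +0.55 | 0.444 | 0.415 | 0.029 |

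Repeat runs put the upper limit at 0.76 to 0.81 SD for 44+16 and 0.49 to 0.55 SD for 46+30. Sample J at 0 is essentially unbiased (0.347 against 0.342; 0.415 against 0.411). The true J at the chosen point averages 0.298 and 0.374, so against that yardstick the optimism is 0.394 - 0.298 = 0.096 and 0.444 - 0.374 = 0.070.

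**In percentage points.** The documents give no marker SD. Five years of age is 5 × 0.54 = 2.7 points, which is 0.54, 0.27 or 0.18 SD if the SD is 5, 10 or 15. At 44+16 the chosen point is more than 2.7 points from 0 in about 8%, 26% and 36% of trials respectively; at 46+30, in about 2%, 12% and 23%.

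**Other shapes.**
- Logistic gradient matched to 68%/25%: maximised J 0.492 and 0.500 against true J at the chosen point of 0.372 and 0.405. Here 0 is not the optimum, so part of the shift is not noise.
- No association: maximised J still averages 0.15 and 0.13 when the truth is 0.

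**Arm mix.** About half of the abnormal patients go to arm C. With abnormal patients halved, sensitivity/specificity at 0 moves from 0.79/0.63 in the whole population to 0.88/0.46. Under the logistic gradient the optimum moves from +0.20 to +0.40 SD. This is a design effect, separate from sampling noise.

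**The case against.** The strongest reply is that this is one item under the SAP's heading of exploratory analyses and that nothing depends on it. That stands, and it rules out several stronger readings that a reader might infer.

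- *The trial adopts a new cut-off.* It does not. Allocation, the primary comparison and T-cell normalisation all use the fixed formula, and no section applies the Youden point to any patient or analysis.
- *The pre-set cut-off goes untested.* Arm A against arm B is the pre-set cut-off. SAP 11.5.1 tests it and gives odds ratios and a difference in proportions with 95% CIs. The Appendix 1 shell tabulates remission by arm, from which sensitivity, specificity and J at 0 follow by arithmetic. What is missing is their presentation as such, their CIs, and any link to the claim of verification.
- *The plan will report inflated accuracy.* SAP 12.1 promises no sensitivity, specificity or J at the chosen point. The optimism applies to the maximised J and to any accuracy quoted there. The AUC is not inflated by the choice of point.
- *The chosen point is never right.* In roughly 21% to 28% of simulated trials it classifies every sampled patient exactly as 0 does. An estimate that differs from its true value is not in itself a defect; leaving out its uncertainty is.

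The J gap of 0.03 to 0.05 is also less than half the sampling SD of J at 0 (about 0.10). None of this supplies an interval for the Youden point or makes the search a verification.

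**Conclusion.** The concern holds within the exploratory ROC analysis. The stated aim is to verify a fixed cut-off, and the stated rule estimates a new one without an interval. With 0 exactly optimal, the chosen point varies over about -0.3 to +0.8 marker SD at 44+16 and -0.3 to +0.5 SD at 46+30, and the maximised J averages 0.03 to 0.05 above J at 0. These sizes rest on a normal marker, a step at 0 and the plan's 42%, 68% and 25%. The upward bias of the maximised J appeared under every shape tried, but its size varied. Any figure in percentage points also needs an assumed SD. The primary result, the allocation and the AUC are not affected.

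**What to change.** In SAP 12.1:

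- Make the pre-set cut-off (age-corrected value 0) the one evaluated, and report its sensitivity, specificity and Youden index with 95% CIs. This is the essential part.
- Change the wording so that the Youden-maximising point is reported as an exploratory estimate rather than chosen as optimal. Give it a bootstrap 95% CI, with candidate cut-offs at midpoints between adjacent observed values, and an optimism-corrected J.
- Do not add a rule that the cut-off is contradicted when that CI excludes 0. In simulations with 0 correct, the CI excluded 0 in 28% to 33% of trials at 44+16 and 18% to 21% at 46+30 when cut-offs sat at observed values. With midpoints this fell to about 6% to 10%, still above the nominal 5%.
- State that the bootstrap does not correct for about half of the abnormal patients going to arm C. Correcting that would need weighting by the inverse of the sampling fraction.

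Cost: a few lines of SAP text and a short bootstrap loop. No new data are needed. Protocol 12.5.3 carries the same rule, so the change should be listed in SAP 13.1.
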